1. Using the geometric mean measured exposed individual based on study 201544 (200 µg top dose Day 1) to generate (linear extrapolation including an increase of 1.71 fold for C_{max} and 1.54-fold on AUC due to formulation differences) the exposure for a 1000 µg Inhaled dose concomitant with a 10 mcg intravenous dose (15 min infusion) (intravenous dose exposures assume 1% of inhaled exposure as worst case) based on a single dose period 1 and following a single oral dose of 800 µg in period 2 (assuming 60:40 lung to oral deposition using study data from 201544 and charcoal block and linear extrapolation). C_{max} and AUC_{0-24h} of 3.5 ng/mL and 14.7 ng.h/mL for Period 1 and a C_{max} and AUC_{0-24h} of 0.47 ng/mL and 3.7 ng.h/mL for Period 2 respectively.
2. Based on the no observed adverse event level (NOAEL) derived from the rat 3 month toxicology study R29876 with a C_{max} and AUC of 43.7 ng/mL and 286 ng.h/mL respectively.
3. Based on the highest achieved geometric mean value derived from reported trials to date of 5.3 ng/mL and 85 ng.h/mL based on exposure on Day 7 following repeat daily single doses (study PII115117).

For more detailed information on the clinical pharmacokinetics, see the GSK2269557 IB [GlaxoSmithKline Document Number [2012N141231_07](#)].

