## 2.3. Study Design

Overview of Study Design and Key Features			
Screening  Within 30 days before first dose	Treatment Period 1  [  C]-GSK2269557 by IV infusion (concomitant with GSK2269557 by inhalation).  Sample collection for 7 days after dosing	At least 14 days washout between doses	Treatment Period 2  Single oral dose of [  C]-GSK2269557.  Sample collection for 7-14 days after dosing*

*If radioactivity excretion is higher than 1% upon discharge, faecal samples will be collected by participants at home after Day 15 (day of discharge/follow-up).
			
Design Features	
 
open-label
 
single centre
 
non-randomised
 
2-period single-sequence crossover
 
mass balance study
 
approximately 6 healthy male participants will be enrolled
 
there will be a washout period of at least 14 days between doses
 
		
Dosing	
 
The investigational drug is nemiralisib (GSK2269557). Each subject will receive a 10 µg radiolabelled version of GSK2269557 ([C]-GSK2269557) microtracer administered by IV infusion, concomitant with an inhaled non-radiolabelled 1000 µg dose of GSK2269557, in period 1 and a single 800 µg dose of [C]-GSK2269557 administered as an oral dose in period 2.
 
		
Time & Events	
 
Refer to Appendix 2: Schedule of Activities
 
		
Treatment Assignment	
 
This is an open label, non-randomised, 2-period single-sequence crossover study.
 
All subjects will receive [C]-GSK2269557 administered as a single IV dose (concomitant with an inhaled non-radiolabelled dose) at period 1 followed by [C]-GSK2269557 administered as a single oral dose at period 2
 
		

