## 8. PHARMACOKINETIC ANALYSES

The plasma pharmacokinetic concentrations will have different nomenclatures dependent on the method of measuring. For measured concentrations of GSK2269557 in blood plasma, the nomenclature [C]-GSK2269557 describes the parent GSK2269557 concentration derived via analysis by liquid chromatography (LC) + Accelerator Mass Spectrometry (AMS), whereas GSK2269557 describes the parent GSK2269557 concentration derived via liquid chromatography-tandem mass spectrometry (LC/MS). It is expected that, for period 1, the radiolabelled iv dose will be measured using LC+AMS and will be labelled “[C]-GSK2269557”, the non-radiolabelled inhaled dose will be measured using LC/MS and will be labelled “GSK2269557”. For period 2, the radiolabelled oral dose will be measured using LC/MS and will be labelled “GSK2269557”. For each period the total radioactivity will be measured by AMS and will be labelled “Total Radioactivity”. However, these methods may be adapted if necessary.

The reconciliation of the PK Case Report Form (CRF) and SMS2000 data will be performed by, or under the direct auspices of, Clinical Pharmacology Science and Study Operations (CPSSO), GlaxoSmithKline.

Derivation of plasma pharmacokinetic parameters for [C]-GSK2269557, total radioactivity and GSK2269557 will be performed by, or under the direct auspices of, Clinical Pharmacology Modelling and Simulation (CPMS), GlaxoSmithKline.

Derivation of urine/faeces total radioactivity parameters will be performed by, or under the direct auspices of Bioanalysis, Immunogenicity and Biomarkers (BIB), PTS IVIVT, GlaxoSmithKline.

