**Table 1** **Derived Plasma Pharmacokinetic Parameters**

Parameter	Parameter Description
AUC(0-t)	Area under the concentration-time curve from time zero to the time of the last quantifiable concentration (C(t)) will be calculated using the linear trapezoidal rule for each incremental trapezoid and the log trapezoidal rule for each decremental trapezoid.
AUC(0-24)	Area under the concentration-time curve from time zero to 24 hours post dose (C(t)) will be calculated using the linear trapezoidal rule for each incremental trapezoid and the log trapezoidal rule for each decremental trapezoid.
AUC(0-∞)	Area under the concentration-time curve extrapolated to infinity will be calculated as: $AUC = AUC(0-t) + C(t) / \lambda_z$
%AUCex	The percentage of AUC (0-∞) obtained by extrapolation (%AUCex) will be calculated as: $[\text{AUC}(0-\infty) - \text{AUC}(0-t)] / \text{AUC}(0-\infty) \times 100$
Cmax	Maximum observed concentration, determined directly from the concentration-time data.
tmax	Time to reach Cmax, determined directly from the concentration-time data.
t½	Apparent terminal half-life will be calculated as: $t_{1/2} = \ln 2 / \lambda_z$
CL(iv)	Total iv clearance will be calculated as: $CL(iv) = \text{Dose(iv)} / \text{AUC}(0-\infty)$ Treatment period 1, analyte [  C]-GSK2269557 only where Dose(iv) is the actual iv dose calculated as [weight of full syringe (g) minus syringe weight after dose (g)] multiplied by nominal concentration (μg/g)
CLr	If Plasma AUC(0-∞) is calculable then $CL_r = \text{Cumulative Ae[urine]} / \text{Plasma AUC}(0-\infty)$ If Plasma AUC(0-∞) is not calculable then $CL_r = \text{Cumulative Ae[urine]} / \text{Plasma AUC}(0-t)$ Where cumulative Ae from excretion data for treatment period 1 and AUC from NCA PK analysis of Treatment period 1, analyte [  C]-GSK2269557 only.
V(c)	Dose(IV) / AUC(0-∞) Treatment period 1, analyte [  C]-GSK2269557 only. Where Dose(IV) is the radiometric dose as described in Table 1 .
V(dss)	Dose(IV) × AUMC(0-∞) / (AUC(0-∞)) Treatment period 1, analyte [  C]-GSK2269557 only. Where AUMC is the area under the moment curve and Dose(IV) is the radiometric dose as described in Table 1 .

Parameter	Parameter Description

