**Table 2** **Derived Urine and Faeces Pharmacokinetic Parameters**

Parameter	Parameter Description
Ae[urine]	Total radioactivity recovered in the urine (Ae[urine]) calculated for each collection interval per subject and treatment period as:  Ae[urine]=(concentration in urine sample x collected sample weight) for each urine collection interval, eg 0-6, 6-24, 24-48, etc.
Cumulative Ae[urine]	Cumulative total radioactivity recovered in the urine (Cumulative Ae[urine]) calculated for each cumulative collection interval per subject and treatment period as:  Cumulative Ae[urine]= summation of Ae[urine] for each urine collection within the cumulative urine collection interval, eg 0-24, 0-48, etc.
Fe%[urine]	% of total dose excreted as total radioactivity (Fe%[urine]) for each collection interval per subject and treatment period, will be estimated as:  Fe%[urine]=(Ae[urine]) for each collection period)/Dose*100.  Where the dose is the radiolabelled [  C]-GSK2269557, that is in period 1 radiometric iv dose, in period 2 radiometric oral dose
Cumulative Fe%[urine]	Cumulative % of total dose excreted as total radioactivity (Cumulative Fe%[urine]) for each cumulative collection interval per subject and treatment period, will be estimated as:  Cumulative Fe%[urine]=summation of Fe%[urine] for each urine collection within the cumulative urine collection interval, eg 0-24, 0-48, etc.

Parameter	Parameter Description
Ae[faeces]	
Total radioactivity recovered in the faeces (Ae[faeces]) calculated for each collection interval per subject and treatment period as
 $Ae[\text{faeces}] = (\text{concentration in faecal homogenate aliquot analysed} \times \text{weight of homogenate aliquot analysed}) \times (\text{total homogenate weight} / \text{collected sample weight})$ 
for each faecal collection interval, eg 0-24, 24-48, etc

Cumulative Ae[faeces]	
Cumulative total radioactivity recovered in the faeces (Cumulative Ae[faeces]) calculated for each cumulative collection interval per subject and treatment period as
 $\text{Cumulative Ae}[\text{faeces}] = \text{summation of Ae}[\text{faeces}]$ 
for each faecal collection within the cumulative faecal collection interval, eg 0-24, 0-48, etc

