### 8.3.2. Summary Measure

A secondary objective is to determine parent GSK2269557 concentration in plasma following a single IV microtracer of [C]-GSK2269557 (concomitant with an inhaled non-radiolabelled GSK2269557 dose) and a single oral dose of [C]-GSK2269557. To assess this, the plasma PK parameters: AUC (0-inf), AUC (0-t), AUC (0-24), %AUCex, Cmax, tmax, t1/2 of parent GSK2269557 ([C]-GSK2269557 and GSK2269557) will be summarised and listed and the volume (Vdss and Vc) and clearance of parent GSK2269557 ([C]-GSK2269557) after IV dose only will be summarised and listed.

Another secondary objective is to estimate the absolute bioavailability of GSK2269557 following inhaled and oral administration. To assess this, the oral and inhaled bioavailability (F) will be summarised and listed.

To assess metabolism, the plasma PK parameters: ML(iv), ML(po), Fg, EH, Fabs will be summarised and listed. To assess exposure and metabolite ratio in humans, the ratio of Parent GSK2269557/total radioactivity will be calculated for the plasma PK parameters: Cmax, AUC(0-t), AUC(0-24) and AUC(0-∞), results will be summarised, listed and statistical analyses will be conducted as described in Section 8.3.4.1. To assess renal clearance, the PK CLr will be summarised and listed if bioanalysis can quantify parent GSK2269557 in urine collection intervals (i.e. if Ae is quantifiable for collection intervals).

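### The SAP's renal clearance formula divides urinary total radioactivity by the plasma AUC of labelled parent, and no urinary parent amount is defined

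*SAP*

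**What the plan says.** The CLr row of SAP Table 1 divides Cumulative Ae[urine] by plasma AUC(0-∞), or by AUC(0-t) when AUC(0-∞) cannot be calculated. It names its sources as follows: "Where cumulative Ae from excretion data for treatment period 1 and AUC from NCA PK analysis of Treatment period 1, analyte" [14C]-GSK2269557 only. SAP section 8 says that this label "describes the parent GSK2269557 concentration derived via analysis by liquid chromatography (LC) + Accelerator Mass Spectrometry (AMS"), so the denominator is labelled parent drug.

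The numerator is defined in SAP Table 2. The interval amount is "Total radioactivity recovered in the urine (Ae[urine]) calculated for each collection interval per subject and treatment period as" urine concentration times sample weight. The cumulative amount is the "summation of Ae[urine] for each urine collection within the cumulative urine collection interval, eg 0-24, 0-48, etc". Both are total radioactivity. Neither document defines a urinary amount of parent.

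SAP section 8.3.2 adds that CLr "will be summarised and listed if bioanalysis can quantify parent GSK2269557 in urine collection intervals". It then explains this condition as Ae being quantifiable for those intervals.

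Protocol sections 5.1.2 and 9.5.2 plan only total radioactivity as the urine measurement in this study and leave metabolite profiling to a separate one. SAP Tables 2.7 and 2.8 (section 11.9.5) and Listing 34 show CLr beside CL(iv) among the [14C]-GSK2269557 parameters.

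**The concern.** Renal clearance of parent needs the same chemical species above and below the line. Here the numerator counts parent plus every labelled metabolite in urine, while the denominator counts parent only. The SAP does not treat the two as interchangeable: its metabolite load, ML(iv), is built from the difference between total-radioactivity and parent AUC in plasma.

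CLr would appear next to CL(iv) under the label of the parent analyte, so a reader would naturally take CLr/CL(iv) as the fraction of parent cleared by the kidney. Protocol section 3.1 gives routes of elimination as a purpose of the study. A value that counts urinary metabolites as parent would overstate the renal route.

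There is also a smaller gap. Table 2 gives one cumulative amount per interval, and the CLr row keeps the same numerator when its denominator is cut short from AUC(0-∞) to AUC(0-t).

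**Working it through.** The documents state no CLr value, so there is no figure to reproduce. The check traces each term and then sizes the two effects separately.

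**Inputs from the documents**
- Numerator: Cumulative Ae[urine], total radioactivity (SAP Table 2).
- Denominator: period 1 plasma AUC of [14C]-GSK2269557, parent by LC+AMS (SAP Table 1 and section 8).
- CL(iv) = Dose(iv)/AUC(0-∞) for the same analyte and period (SAP Table 1).
- Fe[urine] = Ae[urine]/radiometric IV dose (SAP Table 2, written here as a fraction).
- Period 1 urine intervals end at 6, 24, 48, 72, 96, 120, 144 and 168 h. Plasma is sampled at all of these times except 120 and 144 h (schedule of activities, footnotes 6 and 11).

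**Assumed, because the documents do not give them:** the parent share *f* of urinary 14C, and the parent half-life.

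**1. What the formula returns.** On the AUC(0-∞) branch:

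Ae/AUC(0-∞) = (Ae/Dose) × (Dose/AUC(0-∞)) = Fe[urine, total 14C] × CL(iv)

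This holds if the gravimetric IV dose in the CL(iv) row agrees with the radiometric dose used for Fe. Parent renal clearance over the same interval is *f* times this quantity, so

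CLr as written / parent CLr = 1/*f*

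| Assumed parent share *f* | 1.0 | 0.75 | 0.5 | 0.25 | 0.1 |
|---|---|---|---|---|---|
| CLr too high by a factor of | 1.0 | 1.33 | 2 | 4 | 10 |

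**2. Interval effect.** To isolate it, suppose the numerator is already parent, with mono-exponential decline and urinary excretion proportional to plasma AUC. At half-life *h*, the fraction of AUC(0-∞) reached by time *t* is 1 − 2^(−t/h).

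- Ae(0-168 h) over AUC(0-∞), relative to the matched value: 1 − 2^(−168/h).
- Ae(0-168 h) over AUC(0-48 h), relative to the matched value: (1 − 2^(−168/h)) / (1 − 2^(−48/h)).

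| Assumed half-life | AUC(0-∞) branch | Fallback, t = 48 h |
|---|---|---|
| 24 h | 0.99 | 0.992/0.750 = 1.32 |
| 40 h | 0.95 | 0.946/0.565 = 1.67 |
| 60 h | 0.86 | 0.856/0.426 = 2.01 |

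The preferred branch is therefore only slightly low, and the error of any size lies in the fallback.

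**The case against.** The best defence is section 8.3.2. CLr is reported only if parent is quantified in urine, so the inflated value appears only if that result exists and total radioactivity is used anyway. The note under Table 2 also allows parameters to be added. Both points narrow the harm and show that parent was intended. They do not remove the fault. The condition decides whether CLr is reported, not what goes into it. Its explanatory clause uses the symbol Ae, which Table 2 defines as total radioactivity, and the note defines no parent amount. A programmer following the SAP finds only one Cumulative Ae[urine].

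On the interval, it is fair to say that 0-168 h is the natural reading. The CLr row refers to the period 1 excretion data, and protocol section 10.3.1 asks for cumulative urinary recovery over the whole collection period. A reader might infer that the interval is unsettled on both branches. The documents do not support that, and only the fallback lacks a matching rule. Moreover, a profile clean enough to fit the model above to 48 h would often allow AUC(0-∞) to be calculated, in which case the fallback would not be used.

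A reader might also infer a far larger error from an LC/MS urine result. In period 1 the labelled dose is a "microtracer administered by IV infusion, concomitant with an inhaled non-radiolabelled" dose, 10 µg against 1000 µg, and in plasma "the non-radiolabelled inhaled dose will be measured using LC/MS and will be labelled" GSK2269557. An LC/MS parent amount in urine would then be about 1 + 100F times the labelled amount, where F is inhaled bioavailability. Taking F = 1, in line with the protocol's planning note that "intravenous dose exposures assume 1% of inhaled exposure as worst case", gives 101-fold. No passage proposes LC/MS of urine for CLr, the word parent is used in the SAP for both analytes, and that planning note serves a safety margin and does not estimate F. This deserves a one-line caution and no place in the size of the error.

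**Conclusion.** Wrong as written, low severity. The formula pairs total radioactivity in urine with parent in plasma. Followed literally after the section 8.3.2 condition is met, it gives total-14C Fe[urine] × CL(iv) under a parent label.

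The inflation is 1/*f*. The documents do not fix *f*, so no single size can be claimed. The range shown runs from no error, if all urinary 14C is parent, to 10-fold at a 10% share. The fallback adds a further mismatch where it applies; its size rests on the assumed half-lives and the mono-exponential model.

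A reader might infer that the excretion balance is compromised. It is not. CLr was added in the SAP as a secondary parameter, is reported only conditionally and enters no other derivation. The primary Ae and Fe% endpoints are meant to be total radioactivity and are unaffected. Nor is it certain that a wrong CLr will be reported, since without a urinary parent result section 8.3.2 already withholds it.

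**What to change.** - In SAP Table 2, define a separate period 1 amount, Ae[urine, 14C-parent]. Obtain it from LC+AMS of urine, or per interval as total-radioactivity Ae times the radio-profiled parent fraction, in units consistent with the plasma AUC.
- In Table 1, use this amount as the CLr numerator. Keep the AUC(0-∞) branch and state that it takes the 0-168 h amount.
- In the AUC(0-t) fallback, use an Ae and an AUC that end at the same time. The nominal times shared by plasma sampling and urine collection are 6, 24, 48, 72, 96 and 168 h.
- Word the section 8.3.2 condition as 14C-labelled parent, and add one line noting that a period 1 LC/MS urine amount would include parent from the unlabelled inhaled dose.
- If no 14C-parent amount is available, do not report CLr.

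The cost is mostly SAP wording. Aliquots of every urine collection are already taken for profiling, so no new sampling is needed. There are two downsides. CLr would depend on a urine profiling result that SAP section 9 presents as possible and not as committed. The fallback may also need an extra partial AUC when a participant's last quantifiable plasma time is not a urine boundary (for example 8, 12 or 16 h); that output is not among the ten parameters listed under Table 1 for derivation in Phoenix.

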5.1.2. Study Periods

The study will be divided into treatment periods 1 (concomitant IV and inhaled dosing) and 2 (oral dosing). In each treatment period, participants will be resident in the unit from the afternoon before Day 1 (Day -1).

On Day 1 of treatment period 1, after an overnight fast of at least 8 h, each participant will take 1000 µg non-radiolabelled GSK2269557 by inhalation. Within 5 min after the inhalation, participants will receive 10 µg [¹⁴C]-GSK2269557 (approximately 22.2 kBq; 0.6 µCi) by IV infusion over 15 min. Following dosing, blood, duodenal bile, urine and faecal samples will be collected up to 168 h after dosing (Day 8).

Participants will be discharged on Day 8 after completion of the 168-h post-IV dosing sample collection. There will be a washout of at least 14 days after inhaled and IV dosing before participants take the oral dose of GSK2269557 in treatment period 2.

On Day 1 of treatment period 2, after an overnight fast of at least 8 h, each participant will take 800 µg [¹⁴C]-GSK2269557 (50 µCi or 1850 kBq) as an oral solution. Following dosing, blood, urine and faecal samples will be collected for a minimum of 168 h (up to Day 8), but could be up to 336 h (Day 15) or longer after dosing, depending on the amount of radioactivity excreted by each participant. Liquid scintillation counting (LSC) will be performed daily on 24 h urine collections and 24 h faecal homogenates after Day 6 (at 144 h and 168 h from dosing).

- If less than 1% of the dose is excreted in each 24-h period on Day 6 (120–144 h) and Day 7 (144–168 h) for a given participant, that participant may be discharged as early as Day 8 (after the LSC results are available), and no further samples will be collected.
- If excretion is higher than 1%, or if the results are inconclusive in each 24-h period on Day 6 (120-144h) and Day 7 (144-168h) for a given participant, the participant will remain at the unit, and urine and faecal collections will continue at 24-h intervals, for up to 7 days (until the morning of Day 15). If less than 1% of the dose is excreted in any of the 24-h periods between Day 7 and Day 15, that participant will be discharged. All remaining participants will be discharged from the unit on Day 15.
- In the unlikely event that excretion is still higher than 1% upon discharge on Day 15, the participants will continue to collect faecal samples only, at home, at 24-h intervals. Samples will be returned to the unit every 2–3 days for analysis.

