7.1. Treatments Administered

Study treatment			
Study Treatment Name:	[¹⁴ C]-GSK2269557 solution for IV infusion	GSK2269557 Ellipta DPI	[¹⁴ C]-GSK2269557 oral solution
Dosage formulation:	[¹⁴ C]-GSK2269557 hemisuccinate salt (GSK2269557T) in normal saline	GSK2269557 hemisuccinate salt (GSK2269557H) blended with lactose and magnesium stearate ¹ packed in foil blisters	[¹⁴ C]-GSK2269557 hemisuccinate salt (GSK2269557T) in water
Unit dose strength(s)/ Dosage level(s):	10 µg [¹⁴ C]-GSK2269557 (<0.5 µCi) in 10 mL	500 µg GSK2269557 per inhalation / 1000 µg dose	800 µg [¹⁴ C]-GSK2269557 (approximately 50 µCi) in 10 mL
Route of Administration:	IV infusion	Oral Inhalation	Oral
Dosing instructions:	Non-sterile powder is to be dissolved aseptically in 0.9% sodium chloride v/w to a concentration of 1 µg/mL free base equivalent. IV solution is prepared by sterile filtration. 20 mL will be withdrawn into Individual labelled participant specific 60 mL syringes. Only 10 mL of IV solution, equivalent to 10 µg GSK2269557 is then administered intravenously as a single dose over 15 minutes, as soon as possible (within 5 minutes) after the start of the inhaled dose	Inhale TWICE from this Inhaler, as directed.	Non-sterile powder is to be dissolved in sterile water to a concentration of 80 µg/mL. 10 mL of the solution, equivalent to 800 µg, is then administered as a single oral dose. Participants can have up to 250 mL water to wash the dose down
Packaging and Labelling	Labelled drug substance will be provided in High Density Polyethylene (HDPE) containers with polypropylene closure to the site pharmacy.	Study Treatment will be provided in a foil overwrap. Each foil overwrap will be labelled as required per country requirement.	Labelled drug substance will be provided in HDPE containers with polypropylene closure to the site pharmacy.
Manufacturer	GSK	GSK	GSK
Device:		ELLIPTA™ inhaler	

1. Magnesium stearate 0.4% w/w of total drug product

For more information on the preparation of the oral and IV dosing solutions, please refer to the Study Reference Manual (SRM).

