#### 8.1.2. Derived Pharmacokinetic Parameters

Pharmacokinetic parameters will be calculated by standard non-compartmental analysis according to current working practices and using the currently supported version of WinNonlin. All calculations of non-compartmental parameters will be based on actual sampling times.

Pharmacokinetic parameters listed in [Table 1](#) will be determined from the plasma concentration-time data, as data permits, for each subject, analyte (total radioactivity, GSK2269557 and [C]-GSK2269557) and treatment period unless otherwise stated.

Pharmacokinetic parameters listed in [Table 2](#) will be determined from the urine and faeces concentration-time data, as data permits, for each collection interval, subject and treatment period unless otherwise stated.

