6. Sampling times relative to the start of the IV infusion. Blood samples for total radioactivity, [C]-GSK2269557 analysis and cold GSK2269557 analysis will be taken: pre-dose and at 0h (post inhalation and pre-IV infusion), at the end of infusion and at 0.33, 0.5, 0.75, 1, 2, 3, 4, 6, 8, 12, 16, 24, 48, 72, 96 and 168 h after the start of infusion.
7. Background radiation sample taken at screening, Day -1 and pre-dose only.
8. An additional pre-dose blood sample may be taken from 1 participant for preparation of a plasma shipment control (details provided in the SRM).
9. Blood samples for plasma metabolite profiling will be collected at 0.5 h and 4 h after the start of the IV infusion.
10. An aliquot from each urine collection will be taken for metabolic profiling (separate study).
11. Sampling times relative to the start of the IV infusion. Urine will be collected at pre-dose, 0-6 h, 6-24 h then over 24 h collection periods as follows: 24-48 h, 48-72 h, 72-96 h, 96-120 h, 120-144 h, 144-168 h.
12. An aliquot from each homogenised faecal collection will be taken for metabolic profiling (separate study).
13. Sampling times relative to the start of IV infusion The pre-dose faecal collection sample can be collected up to 24 h pre-dose. Afterward faeces will be collected over 24 h collection periods as follows: 0-24 h, 24-48 h, 48-72 h, 72-96 h, 96-120 h, 120-144 h, 144-168h.
14. Entero-Test string device will be swallowed at approximately 3.5 h pre-dose (start of inhaled dose) while participants are in a fasted state and the string removed at about 2.5 h post-dose on Day 1. At about 0.5 h post-dose (i.e. 2 hours before string withdrawal) a food cue will be used to stimulate gall bladder emptying).
15. Meal times are 30 min, 4 h and 10 h post dose on Day 1. On all other days, meals will be served at the standard times for the unit.
16. AEs and SAEs will be collected from the signing of the ICF until the follow-up visit. However, any SAEs related to study participation or a GSK concomitant medication will be recorded from the time a participant consents to participate in the study and until the final follow-up visit contact.

## Schedule of activities for treatment period 2

Procedure	Treatment Period 2 (Oral dosing)									Follow-up (7-14 days post-last dose) 	
	Day										
	-1	1 		2	3	4	5	6	7		
		Pre-dose	Post-dose 0-16 h	24 h	48 h	72 h	96 h	120 h	144 h	168 h	
Admission to Unit	X										

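### The SAP prints V(dss) in its bolus form although the IV dose is a 15-minute infusion; correct the formula and reconcile it with the Phoenix output

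*SAP*

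**What the plan says.** The V(dss) row of SAP Table 1 (section 8.1.2) applies to treatment period 1 and the [14C]-GSK2269557 analyte only. The printed expression begins "Dose(IV) × AUMC(0-∞) / (AUC(0", and the AUC(0-∞) in the denominator is squared. The moment term is explained only by the words "Where AUMC is the area under the moment curve", and the dose is specified as the radiometric one. No infusion time or mean residence time appears in the row.

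The dose is an infusion throughout. Protocol 5.1.2 gives it "by IV infusion over 15 min", and Protocol 7.1 has it "administered intravenously as a single dose over 15 minutes". SAP 2.3 also describes a "microtracer administered by IV infusion". The time origin is fixed in the footnotes to the period 1 schedule (SAP 11.2.1, repeated from Protocol section 2): "Sampling times relative to the start of the IV infusion".

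On computation, SAP 8.1.2 says: "Pharmacokinetic parameters will be calculated by standard non-compartmental analysis according to current working practices". The notes after Table 1 list Vdss among the ten parameters to be derived in Phoenix and passed on for reporting. Neither document says whether the run will use a bolus or an infusion dose setting.

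**The concern.** Dose × AUMC/AUC² gives the steady-state volume only when the whole dose enters at time zero. With an infusion timed from its start, drug molecules enter on average half an infusion length later, and that input time is counted in AUMC/AUC as if it were residence time in the body. The resulting volume is too high in every participant. Averaging over six people does not remove an error that always has the same sign.

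Volume after the IV dose is a secondary endpoint (Protocol section 4), and SAP 8.3.2 says that Vdss will be summarised and listed. The definition should therefore be right, and anyone who recomputes the parameter from the SAP should get the reported value.

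**Working it through.** The documents state no V(dss) value, so there is no figure to reproduce. The check is of the formula.

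**Inputs**
- Printed rule: Dose × AUMC/AUC² (SAP Table 1).
- Infusion length T = 15 min = 0.25 h, so T/2 = 0.125 h (Protocol 5.1.2 and 7.1).
- Time zero is the start of the infusion (SAP 11.2.1). The inhaled dose is unlabelled, so it does not contribute to the labelled analyte.
- MRT and clearance (CL) after IV dosing: not given. The values below are assumptions.

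**Algebra**
1. For a constant-rate infusion timed from its start, AUMC/AUC = MRT + T/2.
2. The quantity wanted is Vss = CL × MRT, with CL = Dose/AUC.
3. The printed rule is CL × AUMC/AUC = CL × (MRT + T/2) = Vss + CL × T/2.
4. The absolute excess is therefore CL × 0.125 h, and the relative excess is 0.125 h/MRT. Both are positive for any positive CL and T.

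**Relative excess by assumed MRT**

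| MRT (h) | 0.125/MRT |
|---|---|
| 1 | 12.5% |
| 2 | 6.25% |
| 5 | 2.5% |
| 12 | 1.0% |
| 24 | 0.5% |
| 48 | 0.26% |
| 72 | 0.17% |

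**Absolute excess.** It is 1.25 L at CL = 10 L/h and 5 L at 40 L/h. The protocol's own prediction gives a ceiling. Its section 5.5.1 predicts a period 1 AUC(0-24h) of 14.7 ng.h/mL from 1000 µg inhaled plus 10 µg IV. With complete bioavailability, CL could be at most 1010 µg ÷ 14.7 µg.h/L ≈ 69 L/h, so the excess would be at most 68.7 × 0.125 ≈ 8.6 L. This rests on that prediction and does not fix MRT.

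**Model check.** Two-compartment models with a 15-minute infusion and assumed parameters give, in closed form:

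| True Vss (L) | CL (L/h) | MRT (h) | Printed rule (L) | With T/2 removed (L) |
|---|---|---|---|---|
| 120 | 10 | 12 | 121.25 (+1.0%) | 120.00 |
| 250 | 40 | 6.25 | 255.0 (+2.0%) | 250.0 |
| 550 | 10 | 55 | 551.25 (+0.23%) | 550.0 |

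Numerical integration of the first model gave the same 121.25 L and 120.00 L.

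Applying non-compartmental analysis to these models at the protocol's nominal sampling times gave 120.43 L (printed) and 119.19 L (corrected) for the first, and 253.72 L and 248.75 L for the second. The gap is still CL × T/2 at the estimated CL. The corrected values fall 0.7% and 0.5% below the truth because of trapezoid and extrapolation error. At an MRT of around 12 h, then, the missing term is about as large as ordinary computational error.

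**The case against.** The strongest reply is that the reported result may never be computed from this line. Vdss is to be exported from Phoenix, and SAP 11.4.3 does not list it among the parameters that the programmer derives. An analysis set up as an infusion, with its duration entered, would include the correction. This stands as a limit on the consequence. A reader might infer that the reported V(dss) will be biased upward. The documents do not support that, because they do not state the software setting. They show only that the printed formula is wrong for this dose. The reply does not rescue the formula: a general reference to standard methods does not override an explicit expression, and an infusion-corrected export would then disagree with the SAP's own definition.

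A second reply concerns size. A reader could take a very short MRT and quote an excess of 12.5% or more. That needs an MRT of 1 h or less, and nothing in the documents points there. Plasma sampling to 168 h and a washout of at least 14 days suggest slower elimination, though they do not prove it.

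A third reply is that nothing depends on the number. SAP 2.4 rules out hypothesis tests and treatment comparisons, and no other Table 1 parameter uses V(dss). Clearance, bioavailability, hepatic extraction and fraction absorbed are untouched. The protocol endpoint names volume without specifying an estimator. All of this is correct, and it keeps the point minor.

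**Conclusion.** The printed V(dss) rule is the bolus form applied to a 15-minute infusion timed from its start. It overstates the steady-state volume by CL × 0.125 h, always upward. The relative size is 0.125 h/MRT: 2.5% at 5 h and about 1% or less at 12 h or more, with MRT assumed in each case. The algebra assumes a constant infusion rate and the planned duration.

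The error is established for the formula, not for the study result. As the SAP stands, either the reported V(dss) carries this small excess, or it is infusion-corrected and does not match the planned definition. Severity is minor, because only a descriptive secondary endpoint changes.

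**What to change.** Replace the V(dss) entry in SAP Table 1 with

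V(dss) = [Dose(IV)/AUC(0-∞)] × [AUMC(0-∞)/AUC(0-∞) − T/2],

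where Dose(IV) is the radiometric dose and T is each participant's recorded infusion duration. Add one sentence stating that the Phoenix analysis is run with the infusion dose setting and that V(dss) is its infusion-corrected estimate.

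Do not shorten the first bracket to CL(iv). The CL(iv) row of Table 1 defines its dose from syringe weights and nominal concentration, whereas the V(dss) row specifies the radiometric dose, so the shorthand would change the dose basis without saying so.

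The cost is one formula and one sentence. No new sample or procedure is needed. The treatment phases in SAP 11.3.1 already rely on treatment start and stop times, and the team should confirm that both are recorded for the infusion. The V(c) row should be checked in the same edit: it is printed as Dose(IV)/AUC(0-∞), which has the units of a clearance. That is a separate point.
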